### **16.5.1. Real-time intraerythrocytic drug levels**

Blood will be collected for intraerythrocytic TFV-DP drug level assays at each follow-up visit. Prior pharmacokinetic/pharmacodynamics studies have established levels for categorization of dosing for interpretation of DBS levels. Given the high adherence requirement for women to achieve protective levels, a threshold of 1050 fmol/punch corresponding to 6 or more doses per week will be used as the threshold for optimal adherence (28, 60). Levels below this threshold will be considered to represent suboptimal adherence and will trigger intensification of adherence support as outlined below.

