The main difference between iNSC and targeted iNSC focused on exploring whether or not PrEP is something the participant wants to continue with (given low drug level and relatedly low afforded PrEP benefit), and if so a strengths-based exploration (when dosing did occur, what facilitated it) precedes exploration of specific barriers to dosing (what specifically prevented consistent dosing), needs are identified, strategies discussed and an adherence plan created. Because participants all engage in iTAB, plans will also emphasize use of iTAB to ask for help. Participants no longer interested in PrEP will be engaged in discussion around that decision and their plan for how to stay HIV negative using other strategies discussed.

PrEP-STEPS is a four-session weekly intervention with two subsequent monthly booster sessions modeled after an evidence-based ART adherence intervention (LifeSteps) which is a Cognitive Behavioral Therapy (CBT)-based counseling approach to facilitate PrEP adherence. This program will be deployed at in-person sessions and is the highest intensity level intervention.

The 3 interventions will be used as three “stages” or levels of intensity of adherence support. One intervention is deployed for a given participant, titrated based on the history and chronology of real-time measured DBS TFV-DP levels.

All participants will receive iNSC at the baseline/entry visit and at all subsequent visits [see the MOPS for structure of the standard iNSC intervention]. Suboptimal adherence (TFV-DP levels of <1050 fmol/punch (representing fewer than mean 6-7 daily doses per week)) will trigger “targeted iNSC” which will be implemented when drug levels are obtained by the site- typically about 10 days after the clinic visit (72). Participants in this sub-optimal range are contact by the counselor, informed of their results and asked to come in for a specific conversation (targeted iNSC). This first level of more intensive support may be deployed by telephone or in person. There will not be additional compensation for participating in these sessions. Details of the targeted iNSC intervention are provided in the MOPS. If this is a repeat sub-optimal level the counselor schedules the participant for the first of 4 (+2 booster) PrEP-Steps sessions.

Details of the PrEP-STEPS Program with Content Optimized for Women program are provided in the MOPS.

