**28.2. Permanent Medication Discontinuation**

Permanent medication discontinuation prior to 48 weeks of treatment should be limited to participants who withdraw consent, have laboratory evidence of acute or chronic HIV infection, are so advised by HIV-treatment experts, or have severe toxicity as noted above.

Such participants should continue to be followed per the protocol SOE (Cohort or seroconversion, as appropriate), even though they are no longer taking study medication.

Additionally, participants who have persistently low TFV-DP levels (<1050 fmol/punch), are referred for targeted iNSC (first instance) and PrEP-STEPS (if followed by a suboptimal (<1050 fmol/punch) TFV-DP level at subsequent visit(s)). Refusal/failure to participate in PrEP-STEP programming by attending  $\geq 1$  visit within 30 days of request by study staff may be considered for medication discontinuation in discussion with the Protocol Chairs.

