### **30.1. Sample Size Rationale**

The LAC-PATH group will enroll 85 women and the CCTG group will enroll 50 women for a total of 135 women who will start PrEP. The target goal of the multimodal triaged adherence intervention for women will be to achieve 90% of women with a DBS level  $> 1050$  fmol/punch at any given time. The proportion and 95% confidence interval will be calculated. If we assume 90% of women with a DBS level  $> 1050$  fmol/punch at any given time and 100 women enrolled in the study, then the 95% binomial distribution confidence interval around the estimate will be 6% (i.e.,  $90\% \pm 6\%$ ).

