#### Hypothesis I

Drug levels will be high among those who persist with PrEP over time, as measured by tenofovir-diphosphate (TFV-DP) level > 1050 fmol/punch at weeks 4, 12, 24, 36 and 48.

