#### Hypothesis II

Intracellular TFV-DP concentrations levels will correlate with self-reported adherence by daily texting through iTAB,

For the primary analysis, we will measure adherence using a drug level cutoff consistent with 6 or more doses per week, as measured by TFV-DP level > 1050 fmol/punch at weeks 4, 12, 24, 36 and 48. This will be in the as-treated group who are on-PrEP (censoring those on permanent or temporary discontinuation). A descriptive analysis of the proportion of women achieving adequate adherence by week of study will be conducted. Baseline versus 48 weeks proportion of adherence will be compared via Fisher's exact test.

**In order to examine drug adherence surrounding the implementation of intensified interventions specific to women receiving targeted iNSC and those receiving PrEP-STEPS we will compare the change in levels pre- and post-intervention.**

Additional sensitivity analyses will be performed using alternative cutoffs of adherence. Intracellular FTC-TP levels will be compared to TFV-DP for discrepancy of recent dosing that would be reflective of the short half-life of FTC (past day) versus the past week of dosing that is informed by the long half-life of TDF.

Subgroup analysis will compare adherence and other outcomes between risk categories of women (e.g. serodiscordant partnerships with and without conception intentions, partner of elevated HIV risk, sex worker, recent STI, injection drug use, PEP users).

Adherence will be measured by self-report using daily text messaging through iTAB. We will validate iTAB reported adherence in women using the TFV-DP levels for correlation with the proportion of positive responses in the 34 days prior to the drug level (i.e. two half lives of TDF) in week 12, 24, 36 or 48 using the Spearman correlation coefficient.

The average days of adherence per week during this time will be calculated as number of days reporting doses taken in past 35 days divided by 35 multiplied by 7 and rounded to the nearest whole number. For each number of days per week of adherence (i.e. 0, 1, 2,3, 4,

5,6 and 7) the TFV-DP will be reported from mean (95% confidence interval) and median (IQR).

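### The primary share above 1050 fmol/punch counts only women on PrEP, low levels can lead to stopping, and no share among all starters is planned beside it

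*Combined protocol and SAP*

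**What the plan says.** The primary analysis in section 30.2 describes, week by week, the proportion of women above the 1050 fmol/punch cutoff. Its analysis set is restricted: "This will be in the as-treated group who are on-PrEP (censoring those on permanent or temporary discontinuation"). This agrees with Hypothesis I: "Drug levels will be high among those who persist with PrEP over time".

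Section 30.1 describes the target more broadly: "The target goal of the multimodal triaged adherence intervention for women will be to achieve 90% of women with a DBS level" above 1050 fmol/punch at any given time. The enrolment sentence in the same paragraph reads "for a total of 135 women who will start PrEP", and the precision statement uses 100 enrolled women. The goal sentence does not say whether women who have stopped PrEP count.

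Three provisions connect a low level with later stopping:

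- Section 16.5.1: a level below the threshold "will trigger intensification of adherence support as outlined below". It does not itself stop the drug.
- Section 16.5.3: the first escalation, targeted iNSC, differs from the standard session in "exploring whether or not PrEP is something the participant wants to continue with (given low drug level and relatedly low afforded PrEP benefit"). The end of the section adds that refusing the adherence interventions may be grounds to consider stopping PrEP.
- Section 28.2: a repeat low level leads to PrEP-STEPS. Refusal, or attending no session within 30 days of the request, "may be considered for medication discontinuation in discussion with the Protocol Chairs".

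The sensitivity analysis named for the share varies only the threshold: "Additional sensitivity analyses will be performed using alternative cutoffs of adherence".

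**The concern.** Women removed from the denominator may be removed because of the quantity being measured. A low week 4 level can prompt a conversation after which a woman stops, and she is then absent from the on-PrEP share from week 12. A second low level at week 12 can lead to a stop that first affects week 24. If stopped women are less often above 1050 than the rest, the by-week share goes up although nobody's adherence has improved.

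This matters because the study has a single arm. A share climbing towards 90% could be read as the staged counselling working, and no comparison group would show how much of the climb is depletion. The on-PrEP share tells a programme how adherent women are while they stay on PrEP. It does not tell it what fraction of the women who start are above the threshold at a given week.

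**Working it through.** **Inputs.** From 30.1: 135 starters, and a precision statement of 90% ± 6% with 100 women. The documents give no stop rate and no expected split of stops by drug level, so the starting shares and stop counts below are assumptions.

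**The plan's own figure.** 1.96 × √(0.9 × 0.1 / 100) = 0.0588, which rounds to the stated 6 points. With 135 women it is 1.96 × √(0.9 × 0.1 / 135) = 0.0506, or 5.1 points.

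**Formulas.** Let A be the number of starters above 1050 if nobody stops, k the low-level women who stop, and h the women above 1050 who stop. Counting stopped women as not above:

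- on-PrEP share = (A − h) / (135 − k − h)
- all-starters share = (A − h) / 135

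The on-PrEP share exceeds A/135 exactly when h/(h + k) < A/135, that is, when stoppers are less often above 1050 than starters as a whole.

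**Starting at 80%: A = 108, 27 low.**

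| k | h | On-PrEP share | Shift from 80.0% | All-starters share |
|---|---|---|---|---|
| 7 | 0 | 108/128 = 84.4% | +4.4 | 108/135 = 80.0% |
| 10 | 0 | 108/125 = 86.4% | +6.4 | 80.0% |
| 14 | 0 | 108/121 = 89.3% | +9.3 | 80.0% |
| 14 | 11 | 97/110 = 88.2% | +8.2 | 97/135 = 71.9% |
| 14 | 54 | 54/67 = 80.6% | +0.6 | 54/135 = 40.0% |

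The last row has about half of each group stopping (14 of 27 and 54 of 108). The on-PrEP share barely moves, although far fewer starters are then above the threshold.

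**Smallest k giving a shift above 6 points, with h = 0.**

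- A = 108 (80.0%): k = 10, 86.4%. With k = 9, 108/126 = 85.7%, a shift of 5.7.
- A = 95 (70.4%): k = 11, 95/124 = 76.6%.
- A = 81 (60.0%): k = 13, 81/122 = 66.4%.

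**Reading back from an on-PrEP share of about 90%.**

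- With 10% stopped: 110/122 = 90.2% on PrEP, and 110/135 = 81.5% of starters.
- With 20% stopped: 97/108 = 89.8% on PrEP, and 97/135 = 71.9% of starters.

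The same headline figure is therefore compatible with quite different results among starters.

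**The case against.** The best defence is that the analysis set is declared and matches its hypothesis. Hypothesis I is about women who persist, the summary is descriptive, and no pass/fail rule is attached to 90%. That stands: a reader might infer that the on-PrEP analysis is invalid, and the documents do not support that.

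A reader might also take the 90% goal as set for all 135 starters. The text does not establish this. The 135 is in a separate sentence, the goal sentence names no denominator, and an on-PrEP reading remains open. The study schema (section 4) likewise speaks of a proportion of women above 1050 without an on-PrEP limit, but it fixes no denominator either.

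Nor does a low level force a stop. It triggers support. Section 28.2 limits permanent stops to a short list and makes stopping for non-attendance discretionary, and 28.1 asks that interruptions be avoided. The largest shifts above also assume no stops among women above 1050, which is an extreme case.

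Section 30.2 has a separate comparison of levels before and after targeted iNSC and PrEP-STEPS. A within-woman change does not rise merely because others leave, so the plan is not silent on the effect of escalation. That comparison can still lose women with no later level, and it does not correct the by-week share.

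Retention and factors associated with discontinuation are planned outcomes. Retention, however, is defined by making a visit, not by being on PrEP. The regression's listed factors do not include TFV-DP, but the list is not said to be exhaustive, so one cannot conclude that the regression would miss depletion.

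Finally, section 30 defers detail to a later SAP that takes precedence. The gap may be closed there, but nothing in the present text commits to doing so.

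**Conclusion.** The point holds as a limit on interpretation. The on-PrEP share is a sound estimate for women who persist. Taken alone, it cannot separate better adherence from the departure of low-level women, and it cannot show whether 90% of starters are above 1050. No planned figure in section 30 fills that gap.

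The size cannot be known from the documents. From an assumed 80% of 135, the shift runs from about zero when both groups stop at equal rates, through 4.4 points with seven low-level stops, to 6.4 points with ten. The last exceeds the planned ±6 points, but both of those figures assume no stops above 1050. Any upward shift requires stoppers to be less often above 1050 than starters overall. The two stop routes make that plausible without proving it.

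The documents do not support making an all-starters figure the single test of the 90% goal. It would mix persistence, missed samples and legitimate stops with adherence. The only 48-week retention figure given, 86–88% in the cited trial in men who have sex with men (section 10), shows the difficulty: if 12% of starters had no sample, the all-starters share could not exceed 88% even with every remaining woman above 1050.

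**What to change.** In section 30.2, or in the formal SAP before database lock:

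1. Keep the on-PrEP share for Hypothesis I and print its denominator at each week.
2. Beside it, report as a supplementary figure the share of all women who started PrEP with TFV-DP above 1050. Count women who stopped, were lost or have no DBS as not above, unless a DBS at that visit is above 1050.
3. Tabulate stops at each week by reason, including toxicity, HIV infection and participant choice, and by whether the last TFV-DP before the stop was below 1050.
4. State which denominator the 90% goal in section 30.1 refers to.
5. State that a rise in the on-PrEP share will not be read as improved adherence without the all-starters figure.

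The cost is a paragraph, a table and a stop-reason code. No new visits or samples are needed. Table 1 already schedules DBS at follow-up visits and at premature discontinuation, and section 28.2 keeps women who stop the drug on the visit schedule. Women who leave the programme need no later sample under rule 2.

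The downside is that the all-starters figure cannot exceed the on-PrEP share unless recently stopped women are still above 1050. It will usually be lower, and it counts legitimate stops as not above. It should therefore sit beside the on-PrEP share, with the stop table, and not replace it.

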#### 4. STUDY SCHEMA

- Design: AEGIS is an open-label single-arm longitudinal clinical trial to estimate medication adherence and retention in a PrEP HIV prevention program that implements a combination intervention strategy that uses text-messages (iTAB) and a staged adherence counseling support strategy titrated from real-time drug levels in women at-risk for HIV acquisition.
- Duration: Each participant will be on PrEP with medication adherence support for 48 weeks after enrollment with a post study follow-up at 60 weeks. The primary endpoint will be measured at 48 weeks.
- Sample Size: A total of 135 participants will be enrolled (50 at CCTG sites and 85 at the LAC-PATH site).
- Study Population: Eligible participants will include HIV-uninfected cis-gender women at least 18 years of age and who are at risk for HIV acquisition.
- Intervention: All participants will be given PrEP with tenofovir disoproxil fumarate (TDF) + emtricitabine (FTC) fixed dose combination prescribed to be taken once daily. All participants will receive the combined intervention of iTAB text messaging adherence reminders and intensive Next Step Counseling (iNSC). The iTAB system consists of daily, personalized, automated 2-way text messages to maintain adherence and retention, and iNSC is a brief, strengths-based discussion initiated at each clinic visit, typically with delivery of negative HIV-test results, focused on promotion of sexual health protection through behavioral and biomedical (adherence) strategies. Participants that have a low intracellular tenofovir diphosphate (TFV-DP) concentration will receive escalated, targeted adherence support (see study schema). All participants will receive access to PrEP in accordance with standardized comprehensive methods of prescribing and clinical assessments that include safety monitoring as well as regular HIV and sexually transmitted infection (STI) screening.
- Regimen: TDF 300 mg + FTC 200 mg fixed dose combination will be given orally once daily starting at the baseline visit (month 0) and continued throughout the study.

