The Partners-PrEP study (a population of heterosexual serodiscordant men and women in Kenya and Uganda) also found that drug levels strongly predicted TDF/FTC and TDF efficacy - detectable drug (using a more sensitive assay than the primary iPrEx data) predicted 86% efficacy for TDF alone, and 90% efficacy for TDF/FTC (contrast 67% and 75%, in the overall population, respectively). The Partners-PrEP study found three distinct patterns of adherence: 1. Seventy percent of participants had sustained TFV drug levels >40 ng/mL; 2. Ten percent of the population had levels that were detectable most of the time (10-40 ng/mL), but dipped occasionally to undetectable levels; and 3) Twenty percent of the population had persistently undetectable drug levels (52). It is probable that prospective, real-time identification of these non-adherent populations (although it remains unclear what percentage this would represent in iPrEx [the MSM population studied to date] – one would suspect the overwhelming majority) and applying intensive adherence interventions would be critical to the success of a PrEP effort.

In this study we will use intracellular TFV-DP from DBS as our primary outcome measure of adherence. Anderson and Castillo-Mancilla have developed technology using LC-MS/MS to measure intra-erythrocytic TFV-DP levels, which provide a measure of average tenofovir exposure (adherence) over the preceding 30-90 days, not unlike a Hemoglobin A1C measurement (53). Such measurements can be made from DBS samples, which are stable over time and easy to handle. The key characteristic that enables TFV-DP to be used as an adherence biomarker is the 17-day half-life of TFV-DP in red blood cells. A similar long-term objective measure of adherence, tightly correlated with virologic suppression has been validated using scalp hair samples (54). However, sampling of scalp hair has proven variably acceptable among diverse populations (unpublished data, ACTG A5257).

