iTAB has found to be associated with high adherence and valid as a measure of self-reported adherence in CCTG 595, an open-label, two-arm, controlled, randomized 1:1 clinical trial of iTAB versus standard of care (no iTAB) as a demonstration project evaluating retention and adherence to PrEP in 400 MSM and transgender women over 48 weeks. In a preliminary analysis of intracellular TFV-DP levels in Week 12 DBS among the first 152 participants in the iTAB arm (71), we found that adherence in the iTAB arm was high with a

mean TFV-DP of 1352 fmol/punch, which equates to taking 6 of 7 doses of PrEP a week. Since CCTG 595 is an ongoing study, the comparison of iTAB to a control arm that did not receive iTAB text has not been performed yet. The preliminary data also show a significant correlation between TFV-DP concentrations and proportion of positive (“Yes, I took my meds.”) iTAB responses ( $r=0.26$ ,  $p=0.01$ ) supporting iTAB as a valid measure of adherence. These findings support the use of iTAB as a valid self-reported measure for adherence that can discriminate between adequate and inadequate PrEP adherence.

In this study, all participants will receive text messaging through the iTAB system. At the baseline visit, the study coordinator will introduce the participant to the iTAB texting system and provide training on iTAB framework for texting supportive reminder messages and tracking adherence. If a participant does not have unlimited text messaging, the study will provide participant reimbursement to pay for unlimited text messages. In cases where a participant does not have a phone, an appropriate cell phone with an unlimited texting plan will be provided.

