## 18. STUDY ASSESSMENTS

The 10 domains to be covered include:

- a. Adherence
- b. Substance Use
- c. Sexual Behavior/Risk
- d. Psychosocial Constructs
- e. PrEP Efficacy
- f. Willingness to Take PrEP
- g. Violence and Trauma
- h. Healthcare and Referrals
- i. HIV Knowledge and Perception
- j. Family Planning

At the screening visit, CASI-based assessments will be administered which will include the domains of Sexual Behavior/Risk, PrEP efficacy, Willingness to take PrEP, Violence and Trauma and HIV knowledge and Perception and Family Planning.

At the baseline visit, additional CASI-based assessments will be administered which include Adherence, Substance Use, Psychosocial Constructs, Violence and Trauma and Healthcare and Referrals.

During follow-up visits (4, 12, 24, and 36 weeks) CASI-based assessments will continue which will include Adherence, Substance Use, Sexual Behavior/Risk, Psychosocial Constructs, Violence and Trauma and Healthcare and Referrals, and Family Planning.

At the End of Study (week 48) visit, CASI-based assessments will include, in addition to above, PrEP efficacy and HIV knowledge and Perception.

Study visits will also include discussions with study staff about substance use, depression and domestic violence. Concern about substance abuse will trigger referral for substance abuse counseling. A screen for depression and/or psychological distress or any request for mental health services will trigger referral for appropriate mental health services. Any report or suspicion of domestic/partner violence will trigger referral for appropriate partner services.

In terms of risk reduction counseling, all participants will be provided a sexual health counseling session at every study visit starting at baseline (see below). All participants will be counseled that condoms should be used for all forms of penetrative non-oral sexual contact.

*Full contents of the CASI and assessments will be specified in MOPS.*

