## 20. SCHEDULE OF CLINICAL AND LABORATORY EVALUATIONS

Table 1. Schedule of Evaluations							
	Screen	Study Weeks of Follow-up				Interim	
	Within 28 days	Baseline	Wk 4	Week 12 and every 12 weeks	End of Study or premature D/C	Suspected HIV or STI infection	Interim for Missed Visit
Visit Window		± 14 days					
Informed Consent	X						
Demographics	X						
Locator Form	X						
Medical/Medication History	X						
Concomitant medications	X	X	X	X	X	X	X
Limited physical exam	X	X	X	X	X	X	X
Clinical assessment	X	X	X	X	X	X	X
Fertility intent assessment	X	X	X	X	X	X	X
Contraceptive counseling	X	X	X	X	X	X	X
Domestic/partner violence assessment	X	X	X	X	X	X	X
Systems review and iTAB setup		X					
PrEP dispensation		X	X	X			
Adherence/ risk reduction/ Sexual health counseling		X	X	X	X	X	X
Self-reported tablet assessments 	X	X	X	X	X	X	X
PrEP adherence assessment			X	X	X	X	X
Laboratory							
HIV EIA/VL or Ag/Ab 	X						
Rapid HIV Test		X	X	X	X	X	X
HBsAg and HBsAb	X						
Urine beta HCG	X	X	X	X	X	X	X
Cr and GFR	X		X	X	X	X	X
LFT and CBC		X					
Serum RPR		X		[X]	[X]	X	[X]
3-site STI Screening		X		[X]	[X]	X	[X]
HSV-2 Screening		X			X 		
DBS for RBC TFV-DP			X	X	X	X	X
Banked plasma specimen 			X	X	X	X	X
HIV RNA, CD4, genotype						X	
Whole blood						X	

Table 1. Schedule of Evaluations							
	Screen	Study Weeks of Follow-up				Interim	
	Within 28 days	Baseline	Wk 4	Week 12 and every 12 weeks	End of Study or premature D/C	Suspected HIV or STI infection	Interim for Missed Visit

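### The one named test of the adherence proportion compares week 48 with a baseline drug level that is never measured, and uses an unpaired test on a single cohort

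*Combined protocol and SAP*

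**What the plan says.** The primary-analysis text in section 30.2 (under Hypothesis II) sets the adherence cutoff at TFV-DP above 1050 fmol/punch, lists weeks 4, 12, 24, 36 and 48, and restricts the analysis to women on PrEP, censoring those who have stopped temporarily or permanently. It plans a descriptive proportion by week and then adds: "Baseline versus 48 weeks proportion of adherence will be compared via Fisher's exact test". Baseline is not defined there.

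Other sections fix what can exist at baseline:

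- Section 4: study drug "will be given orally once daily starting at the baseline visit (month 0) and continued throughout the study".
- Section 16.5.1: "Blood will be collected for intraerythrocytic TFV-DP drug level assays at each follow-up visit".
- Section 20, Table 1: the row "DBS for RBC TFV-DP" is blank at Screen and Baseline and begins at week 4. The row "PrEP adherence assessment" also begins at week 4.
- Section 18: "At the baseline visit, additional CASI-based assessments will be administered which include Adherence". This is self-report.

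Section 30.1 gives a 90% target and a 95% interval of ±6 points with 100 women. It gives no power or effect size for the Fisher comparison. Section 30 says a separate SAP will take precedence; that SAP is not among the documents supplied.

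**The concern.** The sentence names a comparison for which one side has no data, so whoever runs it must decide what baseline means, possibly after seeing results. One choice gives a trivially significant result. The other mixes pharmacokinetic accumulation with behavior.

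The test is also wrong for the design. This is a single-arm longitudinal study, so the two proportions come largely from the same women, while Fisher's exact test assumes independent groups.

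What is at stake is the claim about maintenance. Section 6 treats sustained high adherence in women as critical, and this is the only test named for the adherence proportion over time.

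**Working it through.** **The plan's own figure.** For 90% with n = 100, the half-width is 1.96 × √(0.9 × 0.1 / 100) = 5.88 points, so the stated ±6% reproduces. It does not depend on the Fisher test.

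**Can the test be run?** The proportion is defined by drug level (section 30.2), drug begins at baseline (section 4), and blood spots start at week 4 (section 16.5.1, Table 1). No baseline proportion exists on that measure. Baseline self-report cannot supply a drug-level proportion.

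**Reading 1: baseline set to 0% (an assumption).** Two-sided Fisher p-values:

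| Baseline | Week 48 | p |
|---|---|---|
| 0/100 | 5/100 | 0.059 |
| 0/100 | 6/100 | 0.029 |
| 0/135 | 4/100 | 0.032 |

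If the true week-48 proportion were 10%, the chance of 6 or more among 100 is 0.942. The test would therefore be significant 94% of the time at a level far below the 90% target.

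**Reading 2: week 4 used as baseline.** Section 10 says the property that makes the marker usable "is the 17-day half-life of TFV-DP in red blood cells". With first-order accumulation, the fraction of steady state on day t is 1 − 2^(−t/17):

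| Day | 14 | 28 | 42 | 84 | 168 |
|---|---|---|---|---|---|
| Fraction | 0.435 | 0.681 | 0.820 | 0.967 | 0.999 |

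Days 14 and 42 are the limits if Table 1's ±14-day window applies to week 4.

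Section 16.5.2 cites a week-12 "mean TFV-DP of 1352 fmol/punch, which equates to taking 6 of 7 doses of PrEP a week". That implies 1352 / 0.967 ≈ 1,397 at steady state and 1,397 × 0.681 ≈ 951 at week 4, below the cutoff.

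For proportions, assume log-normal levels with log-SD s from 0.3 to 0.6 (not given in the documents). If 85% of women exceed 1050 at steady state, the week-4 proportion is Φ(1.036 + ln(0.681)/s):

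| s | 0.3 | 0.4 | 0.5 | 0.6 |
|---|---|---|---|---|
| Week-4 proportion | 40% | 53% | 61% | 65% |

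Exact enumeration of the paired outcomes with 100 women and latent correlation 0 or 0.5 gives:

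- Unchanged 85%: Fisher reports a significant rise in 87% to 100% of trials.
- True fall from 85% to 70%: Fisher reports a significant fall in at most 0.25% of trials. Every week-4 value in the table is below 70%, so the fall appears as a rise.

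This bias comes from applying 1050 at week 4, not from Fisher. McNemar on the same two visits reports a rise in 87% to 100% of trials when 85% is unchanged.

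**Pairing, taken alone.** Take 100 complete pairs, no accumulation bias, and correlation measured as phi. The documents give neither the number of pairs nor the correlation.

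| phi | Fisher power, 85% to 70% | Exact McNemar power | Fisher rejection, 80% unchanged | McNemar rejection, 80% unchanged |
|---|---|---|---|---|
| 0 | 67% | 66% | 3.3% | 3.1% |
| 0.3 | 70% | 81% | 1.1% | 3.0% |
| 0.5 | 73% | 94% | 0.3% | 2.8% |

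With positive correlation Fisher is conservative: it loses power and does not create false positives. As one example, suppose 79 women are adherent at both visits, 11 only at the first, 1 only at the second and 9 at neither (90% against 80%). Fisher gives p = 0.073 and exact McNemar p = 0.006.

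**Week 12 against week 48.** A true 85% reads as 82% to 84% at week 12. With that residual bias and phi 0.3, power for a fall to 70% is 60% to 72% with exact McNemar and 46% to 58% with Fisher. An unchanged 85% is rejected by McNemar in 3.5% to 6.8% of trials over phi 0 to 0.5.

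**The case against.** The best defense is that little rests on this sentence. The primary objective is to measure adherence, the by-week analysis is descriptive, and section 30 calls itself brief and defers to an SAP that may already correct the point. That stands, and it limits the severity. It does not make the sentence workable, and an SAP drafted from this text could carry the error forward.

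The largest numbers depend on readings the plan does not state. It says baseline, not week 4. The spread, the number of pairs and the 85%/70% scenario are assumed, and the mean of 1352 comes from a cohort of MSM and transgender women. This is fair: those figures show what a substitute reading would do and do not predict this trial. Nor is 0% at baseline certain, since prior PrEP use is not listed as an exclusion; no sample is scheduled to check it.

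Table 1 also has a tablet-based self-report row marked at Screen and Baseline, with adherence among its domains. It is still self-report and does not supply a drug level.

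The power gain at phi 0.5 is near the best case. For margins of 85% and 70% the largest possible phi is (0.70 − 0.595) / √(0.85 × 0.15 × 0.70 × 0.30) = 0.64. The gain at phi 0.3 is smaller, though still material. Finally, because women who stop PrEP are censored, the two groups overlap largely but not completely.

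**Conclusion.** The concern holds and should be fixed. That no baseline drug level is scheduled, that baseline is undefined, and that Fisher's test ignores the pairing all follow from the documents without assumptions.

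The size of the effect depends on the reading. A 0% baseline makes about 6% adherence at week 48 significant. A week-4 baseline can turn stable or falling adherence into a reported rise, given first-order accumulation, the 17-day half-life and a log-SD of 0.3 to 0.6. Between two on-drug visits without accumulation bias, ignoring the pairing costs about 11 points of power at phi 0.3 and 21 at phi 0.5 in the 85%-to-70% scenario with 100 pairs.

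The by-week proportions from week 12 onward and the ±6% statement are unaffected. The week-4 proportion is not biased by the test, but it carries the same accumulation bias and needs a caveat.

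**What to change.** In section 30.2, replace the sentence with a within-woman comparison of weeks 12 and 48. Use exact McNemar in women with on-PrEP values at both visits, or a logistic GEE over weeks 12, 24, 36 and 48 with robust standard errors. Name which one is the main analysis before the data are seen. Report the change with its 95% confidence interval, and state that the as-treated result applies only to women still on PrEP. Add that the week-4 proportion is read before steady state, and check that the separate SAP says the same.

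Three costs should be written down:

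- McNemar drops women without both values, so report how many. The GEE keeps any woman with an on-PrEP value from week 12.
- Some women will have had targeted counseling before week 12 (section 16.5.3), so the comparison measures maintenance from week 12, not change from before escalation.
- Residual accumulation at week 12 can lift McNemar's rejection rate to 6.8% when nothing has changed. Repeat the comparison with week 24 (99.9% of steady state) in place of week 12 as a sensitivity check.

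The edit is a few sentences. The week 12, 24, 36 and 48 samples are already scheduled, and no visit or clinical rule changes.
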